9.3. Clinical Laboratory Evaluations

Laboratory parameters will be presented in Système International (SI) units.

Local laboratories were used during the original parent study NEOD001-001. A central laboratory (Covance Central Laboratory Services) was used for this open-label extension, NEOD001-OLE001. Data from the local and central labs will not be pooled. Summaries will only present data from the central laboratory for OLE Safety Population.

All clinical laboratory data will be presented in by-subject data listings. In addition, separate listings will be presented for any subject with a post OLE baseline CTCAE Grade 3 or 4 laboratory value.

The following normal ranges will be used where not provided in the central laboratory data:

- INR Upper Limit of Normal (ULN) = 1.1
- eGFR LLN = 90 mL/min/1.73m²

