2.3.3.4. Cardiac Endpoints

The following endpoints will be evaluated in the Cardiac Evaluable Population (see Section 5).

For these subjects, cardiac response, as assessed by N-terminal pro-brain natriuretic peptide (NT-proBNP), categories are defined as (modified from Table 2 in [Comenzo, 2012](#)):

Response	Stable Disease	Progression
Decrease in NT-proBNP from baseline of >30% and >300 ng/L or decrease in NYHA class of ≥ 2 in subjects with baseline NYHA class III or IV	Assessment was neither Response nor Progression	Increase in NT-proBNP from baseline of >30% and >300 ng/L

Best response is defined as the most favorable category (response, stable, or progression) across all visits. Subjects will be classified as responders or non-responders. Non-response is defined as either stable or progression.

- Cardiac response from NEOD001 and OLE baselines (see Section 2.2.4), as assessed by NT-proBNP response criteria, at each visit
- Cardiac best response from NEOD001 and OLE baselines (see Section 2.2.4), as assessed by NT-proBNP response criteria. Best response will be over the course of the study.
- Change and percent change from NEOD001 and OLE baselines (see Section 2.2.4) to each visit in NT-proBNP

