7.2. Demographics and Baseline Characteristics

Demographic and baseline characteristics from as reported on the OLE Demographics eCRF will be summarized for the OLE Safety Population.

Demographic variables will include the following:

- Age at informed consent including the subgroups <65 vs \geq 65 years and <75 vs \geq 75 years
- Sex
- Race
- Ethnicity

Other baseline characteristics will include the following:

- Weight (kg)
- Height (cm)
- BMI (kg/m^2) including frequency of the following subgroups: <20, \geq 20 to <30, \geq 30 kg/m^2

Both conventional BMI and modified BMI (mBMI [$\text{kg}/\text{m}^2 \times \text{g}/\text{L}$], defined as subject's weight (kg)/subjects squared height (meters) \times serum albumin (g/L)) will be presented.

No inferential statistical comparisons will be performed.

All demographic and baseline characteristics data will be presented in by-subject data listings.

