9.4. Weight and BMI

Weight (kg), BMI (kg/m^2), and mBMI ($\text{kg}/\text{m}^2 \text{ g/L}$), defined as a subject's weight (kg) \div subjects squared height (meters) \times serum albumin (g/L), will be summarized using descriptive statistics at NEOD001 baseline, OLE baseline, at each post NEOD001 baseline visit, and at each post OLE baseline visit. In addition, changes and percent changes from NEOD001 and OLE baselines will be presented.

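### SAP 9.4 summarises albumin-based mBMI at and from NEOD001 baseline, although SAP 9.3 bars combining local (parent) with central (OLE) laboratory data

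*SAP*

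**What the plan says.** SAP 9.3 gives the source of the laboratory data. "Local laboratories were used during the original parent study NEOD001-001", whereas a central laboratory "was used for this open-label extension, NEOD001-OLE001". Two rules follow: "Data from the local and central labs will not be pooled", and "Summaries will only present data from the central laboratory for OLE Safety Population".

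The other laboratory summaries keep to these rules. SAP 9.3.1 to 9.3.3 take values, changes, CTCAE shifts and normal-range shifts from OLE baseline. SAP 2.3.1 draws the same line: laboratory change is from OLE baseline, while vital signs and ECG change is from both baselines.

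SAP 9.4 treats weight, BMI and mBMI together. By the formula given there and in SAP 7.2, mBMI is BMI multiplied by serum albumin. All three measures "will be summarized using descriptive statistics at NEOD001 baseline, OLE baseline, at each post NEOD001 baseline visit, and at each post OLE baseline visit". The section adds: "In addition, changes and percent changes from NEOD001 and OLE baselines will be presented". Neither 9.3 nor 9.4 makes an exception for albumin or mBMI.

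SAP 2.2.4.1 makes NEOD001 baseline depend on the time from last parent dose to first OLE dose. If it is 60 days or less, baseline is the last assessment before the first parent infusion. If it is longer, baseline is the last assessment before the first OLE infusion.

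**The concern.** Weight and plain BMI do not depend on a laboratory, so reporting them from both baselines is sound. mBMI does depend on one, and 9.4 carries it along under the same two-baseline rule. A programmer cannot follow 9.4 as written and also obey 9.3.

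If 9.4 is followed, some subjects' OLE-visit change will compare a central albumin with a local one. For those subjects the switch of laboratory coincides with entry to the OLE, so an assay offset cannot be told apart from a true change in nutritional status over time. The OLE database cannot settle the matter. Protocol 6.3.1 says that local results are not collected in the eCRF or clinical database, except pregnancy tests, so it will hold no paired local albumin from which to estimate an offset.

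**Working it through.** The plan states no figure to reproduce. The check sets the sections side by side and then illustrates the size.

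**Step 1. Which laboratory supplies the albumin.** The inputs are SAP 2.2.4.1 (baseline rule) and SAP 9.3 (laboratory by study).

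| Gap, last parent dose to first OLE dose | NEOD001-baseline albumin | Parent visits after that baseline | OLE visits | Change from NEOD001 baseline at OLE visits |
|---|---|---|---|---|
| 60 days or less | local | local | central | central minus local |
| more than 60 days | central | none (they precede this baseline) | central | central minus central |

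Three things follow.

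- Within a subject, sources are mixed only in the first row, and only at OLE visits. Parent visits in that row compare local with local. They still put local data into a summary, which the central-only rule excludes.
- Across subjects, if both rows occur, the NEOD001-baseline line of the mBMI table combines local and central albumin.
- SAP Table 2 counts NEOD001 months from the first dose fixed by 2.2.4.1. The same month line can therefore hold parent-study (local) values from short-gap subjects and OLE (central) values from long-gap subjects.

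The documents do not say how many subjects fall in each row.

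**Step 2. How an offset passes through.** Let d be the central-minus-local albumin offset in g/L, with no true change in weight or albumin.

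- Spurious change in mBMI = BMI × d
- Spurious percent change = 100 × d / baseline albumin, whatever the BMI

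**Step 3. Illustration.** Every value here is an assumption.

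- BMI 25 and albumin 40 g/L give mBMI = 25 × 40 = 1,000. With d = 1 the shift is 25 × 1 = 25 units (2.5%). With d = 3 it is 25 × 3 = 75 units (7.5%).
- 75 kg and 1.70 m give BMI = 75 / 1.70² = 25.95. At albumin 35 g/L, mBMI = 908.3. With d = 1, 2 or 4 the shift is 26.0 (2.9%), 51.9 (5.7%) or 103.8 (11.4%) units.
- Over albumin 25 to 40 g/L and d from 1 to 4 g/L, the percent shift runs from 1/40 = 2.5% to 4/25 = 16.0%. A negative offset gives the same sizes with the sign reversed.

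**Step 4. What is not affected.** Change in mBMI from OLE baseline is central against central. Weight and plain BMI contain no laboratory value.

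**The case against.** The best defence concerns scope. The no-pooling sentence sits in the section on clinical laboratory evaluations, and mBMI has its own section. Pooling could be read as merging results within the 9.3 tables rather than deriving an index. That reading is possible, but the SAP does not state it. The reason for keeping the two sources apart applies equally to an index that is proportional to albumin. On the defence's own reading, 9.4 still needs a clarifying sentence.

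The defence is right on several other matters. A clean result is already planned, because 9.4 also asks for change from OLE baseline. The offset is unknown and may be small. SAP 9.3 speaks of local laboratories in the plural, so offsets could differ in sign between laboratories and partly cancel in a mean. SAP 9 plans no inferential safety comparison unless specified, and mBMI is not among the primary endpoints in SAP 2.3.1.

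A reader might also infer that the same contradiction reaches the organ endpoints, for example "Change and percent change from NEOD001 and OLE baselines (see Section 2.2.4) to each visit in NT-proBNP", and likewise creatinine, proteinuria and eGFR in SAP 2.3.3.5. The documents do not support that. SAP 8 and SAP 11 limit efficacy endpoints to listings, with no summary tables or figures, so nothing in them breaches a rule about pooling and summaries. Comparing across laboratories in those listings calls for caution at most. The safety summaries of serum chemistry already use OLE baseline.

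**Conclusion.** The conflict between SAP 9.3 and SAP 9.4 is real and confined to the mBMI summaries that use NEOD001 baseline or parent-study visits. Within-subject mixing arises for subjects with a gap of 60 days or less, at their OLE visits. Mixing across subjects arises if both gap groups occur.

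It would be tempting to say that every subject's mBMI change is distorted, or that a distortion is known to exist. Neither follows. Under SAP 2.2.4.1, long-gap subjects have central values throughout, and no document reports a between-laboratory difference. The 25 to 75 units (2.5% to 7.5%) rest on an assumed common offset of 1 to 3 g/L at BMI 25 and albumin 40 g/L. The wider assumptions in the working reach 16.0%.

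The table is descriptive, so the point is minor. It is worth correcting because the two sections cannot both be followed and the correction is short.

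**What to change.** In SAP 9.4, state that mBMI and its changes are summarised only at OLE baseline and OLE visits, using central albumin, and that weight and BMI continue to be reported from both baselines. This brings mBMI into line with SAP 2.3.1 and SAP 9.3.1 to 9.3.3.

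If the parent-study mBMI values are wanted, present the parent (local) and OLE (central) segments separately, labelled by laboratory source, with no change computed across them. Add to 9.3 that this display is an exception to the central-only rule.

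The first option takes one sentence and removes some tables. The second takes slightly more text. Either way there is no mBMI change across the two studies. The listing-only cardiac and renal endpoints need no change.

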9.3.1. Serum Chemistry, Hematology, and Coagulation

Quantitative serum chemistry, hematology, and coagulation results will be summarized using descriptive statistics at OLE baseline, each post OLE baseline visit, minimum OLE value, and maximum OLE value. The change and percentage change from OLE baseline will also be summarized.

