1.2 STUDY RATIONALE

[figure not shown]
Unlike other hematologic disorders such as multiple myeloma, the morbidity and mortality of AL amyloidosis is almost entirely related to organ dysfunction and not hematologic parameters. One of the major determinants of prognostic outcome in AL amyloidosis patients is the extent of cardiac involvement; 75% of the deaths are due to cardiac amyloidosis (Merlini et al, 2011). The process of amyloid formation results in cellular injury, tissue damage, and organ dysfunction through mechanisms that are not completely understood. Because the current available treatment options are limited to treatment for the PCD component of the disease, the rate of organ function improvement or stabilization (“organ response”) after achieving hematologic response from chemotherapy regimens is highly variable, ranging from 25% to 78% based on published information (Cibeira et al, 2011; Cohen et al, 2007; Michael et al, 2010). Furthermore, the incidence of treatment-related mortality following high dose melphalan and ASCT was 13% within the first 100 days in patients with AL amyloidosis (Skinner et al, 2004) and with the greatest mortality in patients with cardiac involvement. Though the ASCT approach is effective and results in rapid hematologic response, the average treatment-related mortality in four single-center studies ranged from 21% to 39% (Falk and Dubrey, 2010). Therefore, there is an urgent need to develop a treatment that can directly target the misfolded proteins to increase their clearance and to alleviate direct organ toxicity. Treatments that reduce or eliminate PCD in conjunction with treatments that target toxic soluble aggregates and insoluble amyloid may be of great clinical benefit in the treatment of AL amyloidosis.

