6.1.2 Treatment Period: Months 1 through 36, Day 1 (± 5 Days)

Day 1 assessments may be conducted ± 5 days from Day 1, with the exception of Month 1-Day 1 (i.e., no window is allowed at Month 1).

Subjects will receive 24 mg/kg of NEOD001 as an IV infusion every 28 (± 5) days, i.e., on Day 1 of Months 1 through 36.

All laboratory tests to be done centrally, unless otherwise noted. Refer to the Central Laboratory Manual for complete instructions on collection of samples.

Although central laboratory assessments will be performed each month for study analysis, local laboratory assessments including hematology, chemistry, and urinalysis will be performed for subject management. Results will be reviewed prior to dosing at each month's Day 1 visit to confirm that continued dosing is appropriate.

Subjects who present with symptomatic orthostatic hypotension or systolic BP <85 mmHg, which in the medical judgment of the Investigator would interfere with the subject's ability to safely receive treatment, will have the study drug withheld. If the study drug is withheld and subsequently rescheduled, central laboratory assessments required for that visit will need to be repeated if they were drawn >7 days prior to the rescheduled dosing date. However, a symptom-directed physical examination and vital signs need to be repeated prior to each dosing.

An unscheduled central laboratory collection (i.e., hematology, chemistry, PT/INR, and PTT) will be conducted within 3 days before the first day of a new regimen of chemotherapy.

Prior to Infusion:

The following assessments will be done prior to study drug administration on Day 1 of every month, unless otherwise indicated. Because questionnaires and laboratory samples should be completed prior to the 6MWT, all of the following assessments, at a minimum, should be completed 1 to 2 days prior to Day 1:

- Begin urine collection 24 hours prior to the study visit
- Concomitant medications/therapies
- Assessment of AEs

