6.3 METHODS OF ASSESSMENT FOR SAFETY AND EFFICACY

6.3.1 Clinical Laboratory Evaluations

A central laboratory will be used for this study for analysis of hematology, chemistry (including amylase), PT/INR, PTT, troponin T, NT-proBNP, SFLC, SPEP, SIFE, UPEP, UIFE, urinalysis, and 24-hour urine assessment. Details for the processing of laboratory specimens will be provided in the Laboratory Manual. Local hematology, chemistry, and urinalysis laboratory results will be obtained at the Investigator's discretion for subject management when necessary for obtaining results on a more immediate basis. Local laboratory results should also be obtained and reviewed for a safety assessment prior to each administration of chemotherapy. Central and local pregnancy testing will be conducted as shown in [Table 1](#) and [Section 6](#). A positive urine pregnancy test (local laboratory) is to be confirmed with a serum pregnancy test (central laboratory). Results from local laboratory tests will not be collected in the eCRFs or the clinical database (*exception*: local laboratory pregnancy test results will be collected via an eCRF and in the clinical database).

In addition, a bioanalytical laboratory will be used for this study for the analysis of PK and anti-NEOD001 antibody samples, as well as for the storage of serum samples for future correlative testing ([Section 6.4](#)).

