8.3 ANALYSIS OF SAFETY ENDPOINTS

Safety will be assessed through summaries of AEs, changes in laboratory test results, and changes in vital signs. All subjects who receive one NEOD001 infusion will be included in the safety analysis.

All AE data will be listed by study site, subject number, and visit. Adverse events will be coded using the Medical Dictionary of Regulatory Activities (MedDRA). The incidence of TEAEs occurring on or after treatment on Study Day 1 will be tabulated by MedDRA System Organ Class and Preferred Term, and by severity and relationship to treatment. TEAEs leading to discontinuation and SAEs, including deaths, will be listed separately and summarized.

Descriptive statistics summarizing central laboratory data will be presented for all study visits. Changes from baseline to each study visit will also be summarized.

Additional safety assessments include vital signs and ECGs. Descriptive statistics of the vital sign and ECG parameters will be presented by study visit, as well as the change from baseline at each visit.

The incidence of anti-NEOD001 antibodies will be summarized.

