11. CHANGES TO PROTOCOL PLANNED ANALYSES

Additional analyses of safety endpoints are included in this SAP.

Due to the discontinuation of the NEOD001 program, no summary tables or figures will be produced for the efficacy endpoints.

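### SAP 9.3.1 leaves troponin T and NT-proBNP out of the by-visit descriptive and change-from-baseline laboratory summaries that protocol 8.3 promises, and SAP 11 does not declare the loss for troponin T

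*SAP*

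**What the plan says.** **Protocol.** Section 8.3 (Analysis of Safety Endpoints), like the synopsis, commits to this: "Descriptive statistics summarizing central laboratory data will be presented for all study visits". It adds: "Changes from baseline to each study visit will also be summarized". No panel is excepted. Section 6.3.1 defines what is central: "A central laboratory will be used for this study for analysis of hematology, chemistry (including amylase), PT/INR, PTT, troponin T, NT-proBNP", followed by the light-chain, electrophoresis, immunofixation and urine tests. Section 6.1.2 introduces the monthly list with "The following assessments will be done prior to study drug administration on Day 1 of every month, unless otherwise indicated", and cardiac biomarkers stand in that list with no three-monthly qualifier. Table 1 also shows both markers at Screening and EOS.

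**SAP.** Section 2.3.1 makes change in laboratory assessments from OLE baseline part of the primary endpoint. Section 9.3.1 then provides that "Quantitative serum chemistry, hematology, and coagulation results will be summarized using descriptive statistics at OLE baseline", at each later visit, and as minimum and maximum values, with change and percent change. It names three panels. Appendix 3 lists troponin T and NT-proBNP under a fourth, Cardiac Biomarkers.

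Sections 9.3.2 and 9.3.3 plan shift tables for laboratory tests in general, and 9.3 plans by-subject listings of all laboratory data. Section 2.3.3.4 defines by-visit NT-proBNP change as an exploratory cardiac endpoint. Section 8 makes efficacy endpoints listing-only. Section 11 gives the reason as discontinuation of the program and says that "no summary tables or figures will be produced for the efficacy endpoints". On safety, section 11 declares only additional analyses.

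**The concern.** The study's primary question is long-term safety. Protocol 1.2 says that "75% of the deaths are due to cardiac amyloidosis", and the drug is intended to act on amyloid deposited in organs. Two cardiac markers are drawn at every monthly visit. Under the SAP as written, neither gets a mean, median, extreme value or change from OLE baseline at any visit, although routine chemistry analytes such as uric acid and cholesterol do.

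A gradual upward drift across subjects shows most readily in by-visit change summaries and is hard to see in by-subject listings. For troponin T, a promised safety output is lost without being declared or explained.

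**Working it through.** Neither document states a figure to reproduce. The check is a comparison of text, followed by a count of the results affected.

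**1. Is each marker inside the protocol's commitment?** Protocol 8.3 covers central laboratory data, and protocol 6.3.1 names both markers as central tests. Yes for both.

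**2. Is each marker inside SAP 9.3.1?** That section covers three panels. Appendix 3 of both documents puts the markers in a different panel, and the protocol's visit lists (6.1.1 to 6.1.3) give cardiac biomarkers their own bullet, apart from hematology and chemistry. Reading serum chemistry to include them would go against the documents' own structure. No for both.

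**3. Is the omission declared?** The SAP 11 statement concerns efficacy endpoints.
- NT-proBNP change is one of these (SAP 2.3.3.4), so loss of its efficacy table is declared. Its status as a safety laboratory value is not addressed.
- Troponin T appears nowhere among the efficacy endpoints (SAP 2.3.3.1 to 2.3.3.6), so no declaration covers it.

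**4. What output remains?**

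| Output | Troponin T | NT-proBNP |
|---|---|---|
| By-visit descriptive statistics | none | none |
| Change and percent change from OLE baseline | none | none tabulated |
| Minimum and maximum OLE value | none | none |
| Shift table at each visit (9.3.2 or 9.3.3, general wording) | yes | yes |
| By-subject listing | yes | yes |

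**5. Can a low-normal-high shift table replace the change summary?** Let a subject's OLE baseline be b, with b above twice the upper limit of normal. If the marker doubles, percent change by the SAP 4.5 formula is (2b − b)/b × 100 = +100%. If it halves, percent change is (b/2 − b)/b × 100 = −50%. Both follow-up values are still above the limit, so both subjects are counted as high to high. The table cannot separate them.

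**6. How many results?**
- OLE baseline is the last assessment before the first OLE infusion (SAP 2.2.4.2). Screening and the Month 1 predose draw both come before that infusion, so neither is post-baseline.
- Scheduled post-baseline values per marker per subject: Months 2 to 36 = 35, plus EOS = 1, giving 35 + 1 = 36.
- Subjects: the parent study enrolled 27 + 42 = 69 (protocol 1.3.2), and only those treated for at least 9 months qualify.
- Ceiling per marker: 69 × 36 = 2,484. Ineligibility, drop-out and early termination all reduce it.

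**The case against.** **By-visit summaries do exist.** A reader might infer that the two markers have no by-visit summary at all. The documents do not support that. SAP 9.3.2 covers quantitative laboratory tests in general, with shifts to worst, last, best and each visit, plus counts of Grade 3 or higher and of shifts of two grades or more. SAP 9.3.3 covers the tests that CTCAE cannot grade. Neither is limited to the panels of 9.3.1. This stands, and it narrows the gap to descriptive and change-from-baseline statistics. The SAP does not say which shift table applies to either marker.

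**The weakness of shift tables is not quantified.** A reader might infer that they are uninformative for most subjects. Neither document gives the distribution of either marker at OLE baseline. The 650 ng/L threshold for the Cardiac Evaluable Population (SAP 5) applies to NT-proBNP at parent-study Screening, defines a subset of unstated size, and says nothing about troponin T. The limitation in step 5 is real; how many subjects it touches is unknown.

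**The NT-proBNP half is weaker.** Its by-visit change was planned as an efficacy endpoint, and the SAP openly dropped those tables. That stands, which is why the point rests first on troponin T. It does not answer the separate promise in protocol 8.3, which is a safety analysis.

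**The same literal reading reaches other central tests.** Free light chains, electrophoresis, immunofixation and 24-hour urine results are also in protocol 6.3.1 and outside SAP 9.3.1. This is correct: adding the two markers does not settle the wider mismatch. Singling them out is a judgement, based on the protocol's account of cardiac deaths and on their monthly collection.

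**Cardiac safety is monitored in other ways.** The SAP summarises ECG intervals and QTcF categories (9.6), vital signs (9.5) and adverse events by SOC and PT (9.2). It would be wrong to infer that cardiac safety is unexamined. These outputs do not measure marker levels.

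**Conclusion.** The point holds as a protocol–SAP mismatch limited to descriptive, minimum/maximum and change-from-OLE-baseline summaries. It is clearest for troponin T, where a promised primary-safety output is dropped without declaration. For NT-proBNP, the efficacy table was declared dropped but the safety summary was not addressed.

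The size is at most 36 scheduled post-baseline values per marker per subject in no more than 69 subjects. Multiplying 38 scheduled draws by the planned 70 subjects would give 2,660 per marker, but that counts two pre-infusion draws and exceeds the parent-study enrollment. Either count is only a volume of data; neither measures bias or lost precision.

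The verdict assumes that protocol 8.3 means what it says about central laboratory data and that the panel names in SAP 9.3.1 follow Appendix 3. The mismatch itself is plain. How much it would change the safety conclusions cannot be judged from the documents.

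**What to change.** 1. Extend SAP 9.3.1 to include the Cardiac Biomarkers panel (troponin T and NT-proBNP), with the same OLE baseline, by-visit, minimum, maximum, change and percent-change summaries on central data in the OLE Safety Population.
2. State in SAP 11 that NT-proBNP is summarised as a safety laboratory value while the organ-response endpoints remain listing-only.
3. Say in SAP 9.3.2 and 9.3.3 which shift table applies to each marker.

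If the sponsor prefers not to tabulate the markers, SAP 11 should declare and justify the omission. The same section is the place to declare any other central test in protocol 6.3.1 that will not be summarised.

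The cost is a phrase in 9.3.1, short statements elsewhere, and two more parameters in an existing table program. No new data are needed.
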